11.7. Potential Benefits

There are no medical benefits to the subjects who participate in this study. There is, however, the potential for benefiting future subjects should this study enable the development of improved medical monitoring devices.

11.8. Risk-Benefit Rationale

Medtronic has determined that this is a study of a “non-significant risk device” due to the nature of the devices being tested. Utilizing the FDA criteria^{1,2} listed below to distinguish between significant and non-significant risk devices, Medtronic has determined that:

- The investigational device is not intended as an implant and does not present a potential for serious risk to the health, safety, or welfare of a subject;
- The investigational device is not purported or represented to be for use supporting or sustaining human life and does not present a potential for serious risk to the health, safety, or welfare of a subject;

¹ 21CFR812.2 (b)(1)(ii) and 21CFR812.3(m)

² Information Sheet Guidance For IRB/EC, Clinical Investigators, and Sponsor. Significant Risk and Non-significant Risk Medical Device Studies/January 2006/UMC126418

- The investigational device is not for a use of substantial importance in diagnosing, curing, mitigating, or treating disease, or otherwise preventing impairment of human health, and does not present a potential for serious risk to the health, safety, or welfare of a subject; and
- The investigational device does not otherwise present a potential for serious risk to the health, safety, or welfare of a subject.

The potential risks of these devices have been assessed and are not greater than those of currently approved and marketed devices of the same type (e.g., pulse and tissue oximeters, EtCO₂ monitors, non-invasive blood pressure monitors, ECG or respiration monitors). Society may benefit from more accurate medical monitors.

Medtronic requests that the reviewing IRB indicates its agreement with this determination of non-significant risk device in its letter of approval for this study.

12. Adverse Events and Device Deficiencies

12.1. Adverse Events

AE definitions are provided in **Table 5**. AEs will be collected throughout the study from the BIS™ sensor application through 48 hours following procedure. A list of anticipated adverse events and risks that are expected in nature is included in Section 11.

Adverse Event assessment for the purposes of this study will cease after the follow-up phone call within 48 hours after the procedure. All AEs considered at least possibly related to the study will be followed until resolved, stabilized, and/or returned to baseline.

Reporting of these events to Medtronic will occur on an AE Form. Each event must be reported separately. Documented pre-existing conditions are not considered AEs unless the nature or severity of the condition has worsened.

For AEs that require immediate reporting (see Table 6), initial reporting may be done by phone, fax, or on the CRF completing as much information as possible. The completed AE CRF must be submitted to Medtronic as soon as possible.

Any medication/treatment associated with the treatment of an AE must be reported. Subject deaths are also required to be reported.

12.2. Device Deficiency

The DD definition is provided in **Table 5**. DD information will be collected throughout the study and reported to Medtronic. Note that DD that result in an AE to the subject should be captured as an AE only.

DD that did not lead to an AE but could have led to a SADE (i.e., if suitable action had not been taken, if intervention had not been made, or if the circumstances had been less fortunate) require immediate reporting (see **Table 5**).

12.3. Processing Updates and Resolution

For any changes in status of a previously reported adverse event or DD (i.e. change in actions taken, change in outcome, change in relatedness), information needs to be updated on, or added to the original AE or DD form. All AEs must be followed until the AE has been resolved, is unresolved with no further actions planned, the subject exits the study, or until study closure, whichever occurs first.

In the event that a subject is exited from the study prior to study completion, all efforts should be made to continue following the subject until all unresolved system or procedure related AEs, as classified by the investigator, are resolved, unresolved with no further actions planned, or 30 days post follow up phone call.

At the time of study exit, all collected adverse events that are unresolved must be reviewed and an update to the original AE must be reported.

12.4. Definitions/Classifications

Table 5: Adverse Event and Device Deficiency Definitions

General	
Adverse Event (AE)	
Untoward medical occurrence, unintended disease or injury, or untoward clinical signs (including abnormal laboratory findings) in subjects, users or other persons, whether or not related to the investigational medical device and whether anticipated or unanticipated
 
NOTE 1: This definition includes events related to the investigational medical device or the comparator.
 
NOTE 2: This definition includes events related to the procedures involved.
 
NOTE 3: For users or other persons, this definition is restricted to events related to investigational medical devices.
 
(ISO 14155:2020, 3.2)

Adverse Device Effect (ADE)	
AE related to the use of an investigational medical device
 
NOTE 1: This definition includes AEs resulting from insufficient or inadequate instructions for use, deployment, implantation, installation, or operation, or any malfunction of the investigational medical device.
 
NOTE 2: This definition includes any event resulting from an error use or from intentional misuse of the investigational medical device.
 
NOTE 3: this includes 'comparator' if the comparator is a medical device. (ISO 14155:2020, 3.1)

Device Deficiency (DD)	
Inadequacy of a medical device with respect to its identity, quality, durability, reliability, usability, safety or performance.
 
NOTE 1: DD include malfunctions, use errors and inadequacy in the information supplied by the manufacturer including labeling.

	NOTE2: This definition includes device deficiencies related to the investigational medical device or the comparator. (ISO 14155:2020, 3.19)
Relatedness	
Procedure Related	An AE that occurs due to any procedure.
Seriousness	
Serious Adverse Event (SAE)	
AE that led to any of the following
 
a) death, b) serious deterioration in the health of the subject, users or other persons as defined by one or more of the following:
 
1) a life-threatening illness or injury, or 2) a permanent impairment of a body structure or a body function, including chronic disease, or 3) in-patient or prolonged hospitalization, or 4) medical or surgical intervention to prevent life-threatening illness or injury or permanent impairment to a body structure or a body function,
 
c) fetal distress, fetal death or a congenital abnormality or birth defect including physical or mental impairment
 
NOTE 1: Planned hospitalization for a pre-existing condition, or a procedure required by the CIP, without serious deterioration in health, is not considered an SAE. (ISO 14155:2020, 3.45)

Serious Adverse Device Effect (SADE)	Adverse device effect that has resulted in any of the consequences characteristic of a serious adverse event. (ISO 14155:2020, 3.44)

12.5. Reporting of Adverse Events

12.5.1 Adverse Event and Device Deficiency Classification

All AE and DD will be reviewed by a Medtronic representative. AEs will be classified according to the definitions provided.

Upon receipt of AE at Medtronic, a Medtronic representative will review the AE/DD for completeness and accuracy and when necessary will request clarification and/or additional information from the Investigator. Medtronic will utilize MedDRA for Regulatory Activities, to assign a MedDRA term for each AE based on the information provided by the Investigator.

Regulatory reporting of AEs and DDs will be completed according to local regulatory requirements. Refer to **Table 7** for a list of required investigator and Medtronic reporting requirements and timeframes. It is the responsibility of both to abide by any additional AE reporting requirements stipulated by the EC responsible for oversight of the study.

For emergency contact regarding a UADE, USADE, SAE and/or SADE, contact a study representative immediately (refer to the study contact list provided in the study site's study documents binder/investigator site file or refer to the Sponsor contact information provided on the title page).

AEs and Deaths will be classified according to the standard definitions as outlined below:

Medtronic Controlled Information

Table 6: Adverse Event Classification Responsibilities

What is classified?	Who classifies?	Classification Parameters
Relatedness	Investigator	Device, Procedure
	Sponsor	Device, Procedure
Seriousness	Investigator	SAE, DD with SADE potential
	Sponsor	SAE, UADE/USADE, Complication or Observation (for all system or procedure related adverse events), DD with SADE potential
Diagnosis	Investigator	Based on presenting signs and symptoms and other supporting data
	Sponsor	MedDRA term assigned based on the data provided by Investigator

12.5.2 Adverse Event and Device Deficiency Reporting Requirements

Regulatory reporting of AEs and DDs will be recorded and reported according to local regulatory requirements. It is the responsibility of the Investigator and the sponsor to abide by the AE reporting requirements stipulated by local law and the study site's IRB.

Table 7: Reporting Requirements

Serious Adverse Device Effects (SADE), including Unanticipated Adverse Device Effect (UADE):	
Investigator submits to:	
Medtronic	Within 24 hours after the investigator first learns of the event.
Regulatory Authority	As per local reporting requirements.
IRB	Submit to IRB per local reporting requirement.
Sponsor submits to:	
Regulatory Authorities	Reporting timeframe as per local requirement.
IRB	Submit to IRB per local reporting requirement.
Serious Adverse Events (SAE)	
Investigator submits to:	
Medtronic	Within 24 hours after the investigator first learns of the event.
Regulatory Authority	As per local reporting requirements.
IRB	Submit to IRB per local reporting requirement.
Sponsor submits to:	
Regulatory Authorities	Reporting timeframe as per local requirement.
IRB	Submit to IRB per local reporting requirement.
Adverse Device Effects (ADE)	
Investigator submits to:	

Medtronic	Within 24 hours after the investigator first learns of the event.
Sponsor submits to:	
Regulatory Authority	As per local reporting requirements.
IRB	Submit to IRB per local reporting requirement.
Sponsor submits to:	
Regulatory Authorities	Reporting timeframe as per local requirement
IRB	Submit to IRB per local reporting requirement.
All other AEs	
Investigator submits to:	
Medtronic	Submit as soon as possible, but no later than within 10 working days after the investigator first learns of the event.
Regulatory Authority	As per local reporting.
IRB	Submit to IRB per local reporting requirement.
Device Deficiency with SADE potential	
Investigator submits to:	
Medtronic	No later than 48 hours after the investigator first learns of the event.
Regulatory Authorities	As per local reporting requirements.
IRB	As per local reporting requirement.
Sponsor submits to:	
Regulatory Authorities	As per local reporting requirements.
IRB	As per local reporting requirement.
All other Device Deficiencies	
Investigator submits to	
Medtronic	No later than 48 hours after the investigator first learns of the event.
Regulatory Authorities	As per local reporting requirements.
IRB	As per local reporting requirement.
Sponsor submits to:	

12.6 Product Complaint Reporting

Product complaint reporting and vigilance reporting are applicable and AEs related to any market-released device during the study must be reported. The reporting of product complaints is not part of the study and should be done in addition to the AE reporting requirements. Refer to local regulations for reporting requirements.

Product Complaint: Any written, electronic or oral communication that alleges deficiencies related to the identity, quality, durability, reliability, safety, effectiveness or performance of a medical device that has been placed on the market.

It is the responsibility of the investigator to report all product complaint(s) associated with a medical device distributed by Medtronic, regardless whether they are related to intended use, misuse or abuse of the product. Reporting must be done immediately and via the regular channels for market-released products. The reporting of product complaints by the clinical team must be done according to the local Standard Operating Procedures. Medtronic will notify the RAs (e.g. CA) as applicable for the following incidents immediately upon learning of them and is not limited to AEs and DDs only:

- Any malfunction or deterioration in the characteristics and/or performance of a device, as well as any inadequacy in the labeling or instructions for use which led or might have led to the death or serious deterioration in the state of health of a patient, user, or other person.
- Any technical or medical reason resulting in withdrawal of a device from the market by the manufacturer.
- Any serious deterioration in the state of health, including:
 - Life-threatening illness or injury
 - Permanent impairment of a body function or permanent damage to a body structure
 - A condition necessitating medical or surgical intervention to prevent permanent impairment of a body function or permanent damage to a body structure

13. Data Review Committees

Neither a Data Monitoring Committee (DMC) nor an Adverse Events Advisory Committee (AEAC) will be utilized for this clinical study as there are no safety concerns suggesting the need for a DMC. This study is considered a non-significant risk for study participants. Thus, the need for additional safety oversight

beyond Medtronic's already rigorous safety monitoring processes is not required. A Medtronic Medical Advisor, as needed, will provide an independent medical review according to the study Safety and Complaint Management Plan. The Medical Advisor will not be affiliated with an investigative center.

14. Statistical Design and Methods

The statistical analyses will be conducted by Medtronic or its designee as outlined in the Statistical Analysis Plan (SAP.) Any changes in statistical methods will be detailed in the Clinical Study Report (CSR) Data exclusion will be captured in the Data Management Plan.

14.1. Sample Size Justification

A two-stage adaptive design is used in this study. For each regimen, 10 subjects will be enrolled in stage 1, and upon evaluation, up to 20 additional subjects will be enrolled in stage 2. With 5 regimens, a maximum of 150 subjects will be expected. Based on the dose-response relationship (logistic model) with an allowable error of $\pm 15\%$ for BIS₅₀ and a coefficient of variation of 25% at the alpha level of 0.05, the sample size will provide sufficient power (>80%) to evaluate the performance of anesthetic agents.

14.2. Analysis Populations

All randomized subjects will be included in the analysis. For those subjects who do not complete a follow-up call, the analysis will include all data up to the last collected point or follow-up call. Subjects who completed the procedure phase will not be replaced. If the subject discontinues prior to randomization or during the procedure phase, she/he will be replaced, but will count toward the total sample size if they were randomized.

14.3. Statistical Methods

Standard demographic information and baseline characteristics will be summarized using descriptive statistics.

For safety assessments, adverse events (AEs) will be summarized using frequency counts and percentages. Descriptive statistics will be provided by severity and relationship as needed.

Any subject who responds to any verbal command with MOAA/S assessment scores of 2, 3, 4, and 5 will be considered as responsive. Subjects with MOAA/S assessment scores of 0 and 1 will be considered unresponsive. Tetanic Electrical Stimulation (TES) will be employed with an MOAA/S assessment score of ≤ 2 for the first two subjects in each group and <2 for all other subjects.

The BIS™ index value collected from the left side of the brain will be used for primary analysis to reflect the typical operation of the device from this study. The BIS™ index value collected from the right side of the brain will be used for internal research purposes.

The logistic model (simplified Sigmoid E_{max} model) will be used to analyze the relationship between the BIS™ index and loss of responsiveness through the probability of response curves. The values of BIS™ at which 50% (BIS₅₀) and 95% (BIS₉₅) of subjects are unresponsive, and their 95% confidential intervals will be derived. The systematic variance between groups will be evaluated. The Prediction Probability score (P_k) for correctly predicting if the subject was responsive or unresponsive will be assessed.

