	
Healthy Volunteer Subjects will be randomized to one of the anesthetic regimen groups. The BIS™ bilateral sensor will be placed on the subject's forehead to study the effects of these drugs on the brain. Each subject will be given a sequence of dose ranges of the target drug to achieve targeted drug concentration.
 
If required, a training group, comprising of the first 2 - 4 subjects at each site will be enrolled to train the site team on the technology and to determine the quality of data collection, as required, prior to randomization. Afterward, randomization will proceed based on the Sponsor's assessment of data quality.
 
The Modified Observer's Assessment of Alertness/Sedation (MOAA/S) scale will be used at each steady-state step to measure the level of alertness in sedated subjects. Subjects will then be assessed using a Picture Recall assessment with a standardized set of pictures. Tetanic Electrical Stimulation (TES) will be used once the patient is unresponsive to painful stimuli (e.g., MOAA/S = 0, BIS™ < 40).
 
TES will then be initiated once the subject reaches a MOAA/S = 0, BIS™ value < 40 at the highest concentration of anesthesia anticipated, with an increasing stimulation starting at 20mA, 50 Hz delivered for 1-5 seconds. If the subject does not purposefully (i.e. attempting to push the stimulus away) respond, the stimulation will increase to 30mA, 50Hz for 1-5 seconds, then 40mA, 50 hertz (Hz) for 1-5 seconds and finally to 50mA, 50Hz for 1-5 seconds. If there is still no purposeful response, the subject will be considered a non-purposeful responder (i.e. exhibiting a reflex withdrawal, facial grimace, or groan) and their response such as withdrawal of extremity, facial grimace or other will be recorded along with the BIS™ value prior to stimulation, at the end of all stimulation and approximately 2 minutes later, to allow for equilibration, following stimulation. If the subject does respond to any of the stimulations with a purposeful response, the TES will be ended, the response will be noted and the BIS™ value will be recorded at the time TES is ended and at approximately 2 minutes following the stimulation. Anesthesia will then be decreased in the same steps until subject is conscious.

Randomization	Once enrolled, subjects will be equally randomized to one of the anesthetic regimen groups.

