5.1. Objectives

Primary Objective(s)

To determine BIS₅₀ (BIS™ value at which 50% of patients will be unresponsive at a given drug concentration)

Secondary Objective(s)

To determine BIS₉₅ (BIS™ value at which 95% of patients will be unresponsive at a given drug concentration)

To determine Prediction Probability (P_K) for correctly predicting if the subject was responsive or unresponsive.

6. Study Design

This is a prospective, randomized study to collect data to evaluate the relationship between BIS™ and inhaled anesthetics without and with opioids. Five groups of anesthetic regimens will be studied as follow:

1. Sevoflurane alone
2. Sevoflurane with Remifentanil
3. Sevoflurane with Fentanyl
4. Desflurane alone
5. Isoflurane alone

Healthy Volunteers Subjects will be randomized to an anesthetic group. The BIS™ bilateral sensor will be placed on the subject's forehead to study the effects of these drugs on the brain. Each subject will be given a sequential dose range of the target drug to achieve targeted drug concentration. At each steady-state step, and after at least 12 minutes to achieve equilibrium, the Modified Observer's Assessment of Alertness/Sedation (MOAA/S) scale will be used to perform sedation/loss of consciousness assessment, with the Picture Recall test being used in the sevoflurane, sevoflurane with remifentanil and sevoflurane with fentanyl regimens to assess the subject's level of anesthesia awareness, and Tetanic Electrical Stimulation (TES) being used if the patient is unresponsive to tactile stimuli (e.g., MOAA/S = 0, BIS™ value

< 40 at the highest concentration of anesthesia anticipated). The loss of tactile response will be defined according to the MOAA/S score value < 2 (0-1) and the presence of verbal response at values >2 (2-5).

A training group, comprising of the first 2 - 4 subjects at each site will be enrolled to train the site team on the technology and to determine the quality of data collection, as required, before randomization. Afterward, randomization will proceed based on the Sponsor's assessment of data quality.

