Subjects will have the effect of noxious electrical stimulation on the sedation state assessed for each arm once they achieve an MOAA/S score = 0, BIS™ value <40 at the highest concentration of anesthesia anticipated. The baseline BIS™ value will be recorded, followed by the MOAA/S assessment. Once TES is initiation, stimulation will start at 20mA, 50 Hz delivered for 1-5 seconds. If the subject does not purposefully (i.e. attempting to push the stimulus away) respond, the stimulation will increase to 30mA, 50Hz for 1-5 seconds, then 40mA, 50Hz for 1-5 seconds and finally to 50mA, 50Hz for 1-5 seconds. If there is still no purposeful response, the subject will be considered a non-purposeful responder (i.e. exhibiting a reflex withdrawal, facial grimace, or groan) and their response such as withdrawal of extremity, facial grimace or other will be recorded along with the BIS™ value prior to stimulation, at the time of each stimulation and approximately 2 minutes following each stimulation. If the subject does respond to any of the stimulations with a purposeful response, the TES will be ended, the response will be noted and the BIS™ value will be recorded at the time TES is ended and at approximately 2 minutes following the stimulation. LMA should be removed at this point, if allowed per Investigator's assessment without risk to subject. Anesthesia will then be decreased in the same steps until subject is conscious. An anesthesiologist authorized to administer sedation drugs will be responsible for administering any procedural drugs for the sedation and monitoring of subject safety and physical state. All other personnel involved with the safety monitoring of subjects must be trained in and familiar with the management and recovery of sedated patients. The study site should utilize a setting that is fully equipped for the monitoring and support of the subject's respiratory and cardiovascular functions. Subjects will be continuously monitored throughout the study.

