The Evaluation of BIS™ and Levels of Sedation in Health Volunteers (OLIVER) Study is a multi-center, prospective randomized study to collect data to evaluate the relationship between BIS™ and inhaled anesthetics without and with opioids. Healthy Volunteers will be sequentially assigned to one of the study groups of anesthetics regimens at each clinical site. The BIS™ bilateral sensor will be placed on the subject's forehead to study the effects of these drugs on the brain. Each volunteer will be given a dose range of sequences of the target drug to achieve targeted drug concentration. Five groups of anesthetics regimens will be studied as follows:

1. Sevoflurane alone
2. Sevoflurane with Remifentanil
3. Sevoflurane with Fentanyl
4. Desflurane alone
5. Isoflurane alone

At each steady-state step, and after at least 12 minutes to achieve equilibrium, the Modified Observer's Assessment of Alertness/Sedation (MOAA/S) scale will be used to perform sedation/loss of consciousness assessment. The loss of verbal response will be defined according to the MOAA/S score value < 2 (0-1) and the presence of verbal response at values ≥ 2 (2-5).

The expected duration of each subject's participation is approximately 6 hours for both enrollment and procedure. The Enrollment Visit should take approximately 2 hours to complete, and the Study Visit will be approximately 4 hours per subject. Each subject will be contacted by phone within 48 hours of the study participation. Subjects will be continuously monitored throughout the study.

This document provides a detailed description of the statistical methods and procedures to be implemented during the analysis of the study.

This statistical analysis plan (SAP) is based on Version 5.0 of the Protocol dated on 06-JAN-2022.

4 Study Objectives

4.1 Primary Objective:

To determine BIS₅₀ (BIS™ value at which 50% of subjects will be unresponsive at a given drug concentration).

4.2 Secondary Objective:

To determine BIS₉₅ (BIS™ value at which 95% of subjects will be unresponsive at a given drug concentration).

[BIS] Statistical Analysis Plan

Revision [\[x\]](#)

Page 6 of 20

Form

Medtronic

To determine Prediction Probability score (P_k) for correctly predicting if the subject was responsive or unresponsive.

5 Investigation Plan

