7.2.1 BIS™ Value Analysis

Study subjects will be sequentially assigned to one of the target groups of anesthetics regimens while having BIS™ VISTA Monitoring System, the 4 Channel BISx, and BIS™ bilateral sensor placed on their forehead during these regimens to study the effects of these drugs on the brain. Each subject will be given a dose range of sequences of the target drug to achieve targeted drug concentration.

The modified Observer's Assessment of Alertness/Sedation (MOAA/S) scale will be used to perform sedation/ loss of consciousness assessment. Any subject who responds to any verbal command with MOAA/S assessment score of 2, 3, 4, and 5 will be considered as responsive. Subjects with MOAA/S assessment score of 0 and 1 will be considered unresponsive. Tetanic Electrical Stimulation (TES) will be employed with an MOAA/S assessment score of ≤ 2 for the first two subjects in each group and < 2 for all other subjects.

The BIS™ is a variable derived from the electroencephalograph (EEG) that has been reported to have the ability to measure the hypnotic component of the anesthetic state. It is a dimensionless number from 0 to 100, and decreasing values indicate more sedation and hypnosis.

The BIS™ index value collected from the left side of the brain will be used for primary analysis to reflect the typical operation of the device from this study. The BIS™ index value collected from the right side of the brain will be used for internal research purposes.

The logistic model (simplified Sigmoid E_{max} model) will be used to analyze the relationship between the BIS™ index and loss of responsiveness through the probability of response curves. The values of BIS™ at which 50% (BIS_{50}) and 95% (BIS_{95}) of subjects are unresponsive, and their 95% confidential intervals will be derived. The systematic variance between groups will be evaluated.

The logistic model is as follows:

$$P = \frac{e^{a+bX}}{1 + e^{a+bX}}$$

where P is the probability of “unresponsive”, X is the explanatory variable (BIS™ value or anesthetic agent concentration on the log scale), and a & b are model parameters.

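### Protocol 14.3 and SAP 7.2.1 carry a looser trigger for the tetanic stimulus than the procedures do; the propofol lead-in text for isoflurane and desflurane also needs reconciling

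*Protocol*

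**What the plan says.** **TES trigger.** Protocol 14.3 states that TES "will be employed with an MOAA/S assessment score of ≤ 2 for the first two subjects in each group", with a cut-off below 2 for later subjects. No BIS value or concentration step is attached. The same paragraph says that "MOAA/S assessment scores of 2, 3, 4, and 5 will be considered as responsive". SAP 7.2.1 repeats the rule, "for the first two subjects in each group and < 2 for all other subjects", and SAP Section 3 gives its basis: "This statistical analysis plan (SAP) is based on Version 5.0 of the Protocol". The rule is therefore current text in both documents.

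The procedural text is stricter. Section 6 applies TES in each arm "once they achieve an MOAA/S score = 0, BIS™ value <40 at the highest concentration of anesthesia anticipated". The synopsis sets the same condition for the overall design and for each of the five regimens. Section 10.5 sets it in its general TES text and again under each regimen.

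Two sentences are softer. The synopsis overview says TES "will be used once the patient is unresponsive to painful stimuli (e.g., MOAA/S = 0, BIS™ < 40", and Section 6 describes it as "being used if the patient is unresponsive to tactile stimuli (e.g., MOAA/S = 0, BIS™ value". Both offer the scores only as examples. Section 6 adds: "The loss of tactile response will be defined according to the MOAA/S score value < 2 (0-1".

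**Propofol lead-in.** For isoflurane, the synopsis places the bolus 0 to 15 minutes before the agent and Section 10.5 places it 15 to 20 minutes before. For desflurane, both give 0 to 15 minutes. Section 10.5 alone adds, for both agents, a wait of roughly 15 to 20 minutes after laryngeal mask (LMA) placement is confirmed, to reach MOAA/S 2 or 3. That wait is subject to the investigator's discretion and to safety.

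**Isoflurane details.** Two ascending steps differ: 0.2% and 0.7% in the synopsis, 0.25% and 0.75% in Section 10.5. The synopsis also has a stray 'not' that reverses the instruction to reach a BIS of at least 40.

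**The concern.** Appendix A defines MOAA/S 2 as a subject who still reacts to mild prodding or shaking. TES starts at 20 mA and can rise through 30 and 40 to 50 mA. A rule that allows it at a score of 2, at any BIS and any step, allows a noxious stimulus in a healthy volunteer who by the plan's own definition is responsive.

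Compliance is also affected. Protocol 10.10 requires conduct according to the protocol, yet TES given at MOAA/S 1 meets 14.3 and breaches 10.5. A site or monitor cannot tell from the document alone whether that is a deviation.

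The propofol text matters for a different reason. The wait in Section 10.5 exists so that propofol can fall to a level compatible with consciousness before the study agent starts. If the synopsis is followed, early ascending readings in the arms labelled desflurane alone and isoflurane alone carry more residual propofol. Those readings feed the logistic fits in SAP 7.2.1, which have no propofol term.

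**Working it through.** No sample size or power figure is involved. The check compares current passages and does some simple counting.

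**1. Trigger sets**

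| Source | MOAA/S | BIS | Concentration |
|---|---|---|---|
| Synopsis (design and all five regimens) | 0 | below 40 | highest anticipated |
| Section 6, noxious stimulation paragraph | 0 | below 40 | highest anticipated |
| Section 10.5 (general text and all five regimens) | 0 | below 40 | highest anticipated |
| Protocol 14.3 and SAP 7.2.1, first two per group | 0, 1 or 2 | none stated | none stated |
| Protocol 14.3 and SAP 7.2.1, all others | 0 or 1 | none stated | none stated |

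The set in the last two rows strictly contains the procedural set, so the statistical sections are looser for every subject.

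**2. Subjects under the ≤2 rule**

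Inputs: 2 subjects per group, 5 groups, a maximum of 150 subjects (Protocol 14.1), three to four sites (synopsis), randomization stratified by site (10.5).

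- Counted study-wide: 2 × 5 = 10, or 10/150 = 6.7%.
- Counted per site, three sites: 2 × 5 × 3 = 30, or 20%.
- Counted per site, four sites: 2 × 5 × 4 = 40, or 26.7%.

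The remaining 140, 120 or 110 subjects fall under the <2 rule, which still admits MOAA/S 1 at any BIS. These are numbers governed by the wording and not expected exposures. The per-site counts also assume that every site enrolls at least two subjects in each group.

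**3. Does TES response enter the primary or secondary analyses?**

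Protocol 14.3 and SAP 7.2.1 define responsive and unresponsive by MOAA/S alone. BIS50, BIS95 and Pk are built on that binary outcome. TES response is in none of them.

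**4. Propofol timing**

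Nominal time from the initial bolus to the first on-agent reading = time from bolus to agent start + about 12 minutes of equilibration.

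- Synopsis, either agent: 0 + 12 = 12 minutes up to 15 + 12 = 27 minutes.
- Section 10.5 with the full wait, either agent: at least 15 + 12 = 27 to 20 + 12 = 32 minutes, plus the time to place the LMA.

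The two stated isoflurane lead-ins (0 to 15 and 15 to 20) share only the 15-minute endpoint. For desflurane the stated lead-in is the same in both places; the tension is between 0 to 15 minutes and an added wait of about 15 to 20 minutes that begins only after the LMA is confirmed.

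**The case against.** The strongest reply is that conduct follows the procedures, which are uniformly strict, while 14.3 and SAP 7.2.1 are statistical text. The version history records a version 4.0 change to TES timing made for adequate sedation, which supports reading the sentence as one that was not updated. TES given at MOAA/S 0 under 10.5 also satisfies the looser cut-offs. Scoring MOAA/S 0 or 1 already involves a painful trapezius squeeze, and TES stops at the first purposeful response, so the added burden at a score of 1 is modest. All of this stands and limits the practical risk. It does not remove a conflicting trigger from two current documents.

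Section 6's definition of lost tactile response as a score below 2 agrees with Appendix A and is not itself a TES trigger. It does make the nearby example-only wording easier to misread.

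A reader might infer more than the documents support:

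- *That responsive volunteers will be stimulated in a known number.* The counts depend on an unstated counting rule, and the operational text points the other way.
- *That the primary result is biased by the TES wording.* TES response is not an analysed outcome for BIS50, BIS95 or Pk.
- *That the desflurane instructions cannot be followed.* The wait is approximate and discretionary. If it is not used, 0 to 15 minutes stands without contradiction.
- *That the propofol text shifts BIS50 or EC50 by some amount.* In the BIS50 fit the explanatory variable is BIS itself, and residual propofol can move both BIS and responsiveness. No size can be calculated from the documents, and EC50 is neither a primary nor a secondary objective.

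**Conclusion.** The TES inconsistency is real. Protocol 14.3 and SAP 7.2.1 state a looser trigger than every firm procedural statement and, read literally, permit a noxious stimulus in a volunteer classed as responsive. It is a safety and compliance error. The text brings 10 subjects under the ≤2 rule if counted study-wide, or 30 to 40 if counted per site; actual exposure is likely rare, on the assumption that sites follow Section 10.5.

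The propofol point is secondary. The isoflurane lead-in conflicts directly between synopsis and Section 10.5. The wait for MOAA/S 2 or 3 is missing from the synopsis for both agents. For desflurane, 0 to 15 minutes fits poorly with that wait, which is a weaker conflict. The isoflurane step mismatch and the stray 'not' are plain text errors.

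**What to change.** **TES.** In Protocol 14.3 and SAP 7.2.1, replace the sentence with: TES is given at MOAA/S = 0 and BIS <40 at the highest anticipated concentration. Remove the e.g. in the synopsis overview and in Section 6 so that the condition is firm throughout.

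**Propofol.** Make the synopsis match Section 10.5. Isoflurane or desflurane starts after confirmed LMA placement and the wait of approximately 15 to 20 minutes to MOAA/S 2 or 3, subject to the investigator's safety discretion. Drop the 0 to 15 minute text for both agents, including under desflurane in 10.5. This reduces residual propofol in the early ascending readings but does not remove it, since subjects at MOAA/S 2 or 3 are still sedated by propofol when the agent starts.

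**Isoflurane text.** Use one set of steps (0.2/0.7 or 0.25/0.75), and correct the synopsis so that BIS is taken to at least 40 but not intentionally below 30.

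**Cost.** A small protocol amendment with a matching SAP edit, IRB approval (Protocol 16.6) and retraining of site staff on the current plan (Protocol 8.2). Applying the wait consistently may lengthen some visits for the two propofol-induced arms. No new data or analyses are needed.
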